This study is designed to determine whether SeraSeal is safe, effective, and will improve the quality of care, in achieving hemostasis in surgical wounds or other emergent hemorrhagic episodes. The effectiveness will be determined by achieving hemostasis after application of the product. The safety will be determined by monitoring outcomes from application: recurrence of bleeding, infection, lack of healing, and presence of hypersensitivity reactions, e.g. pruritus, fever, rash, anaphylaxis. An improved quality of care will be achieved by reducing or eliminating the hospital length of stay.

Characteristics of SeraSeal

SeraSeal is a bovine protein-derived accelerator of hemostasis interacting with the intrinsic and extrinsic pathways. It is obtained from pathogen and prion free cows. SeraSeal can be provided as a solution, spray, foam, incorporated into an absorbable dressing or a non-absorbable removable dressing. Its active ingredients are the bovine proteins Factors II, VII, IX, and X.

Toxicity of SeraSeal

A total dosage level of SeraSeal over 13,000 IU/Kg (2.4 mg protein) in leporids and canines had no adverse effects¹⁴. The total expected treatment levels to be used in this study is less than 1,000 IU/Kg, a 130 fold lower level than the no toxic effect. Cell culture studies reveal that SeraSeal is not directly toxic for any cells tested. Thus, drug related toxicity is not expected to be seen in this clinical study.

6.6 Research Design and Methods: This clinical trial will be a difference study where SeraSeal will be used as a liquid, administered by a syringe (300 IU/0.1ml), and compared to standard surgical technique as the control. Patients receiving treatment at Edgardo Rebagliati Martins Hospital, the National Guillermo Hospital, Peruvian Air Force Hospital, and the Military Hospital of Peru will serve as study volunteers. Prior to enrollment in the study, an initial screening test and subsequent studies will take place, including: informed consent, collection and recording of subject demographic information, medical history, current medications, assessment of inclusion/exclusion criteria, physical examination, with blood draws for hematological assessment and coagulation studies for bleeding and time to hemostasis. The location of the study wounds will be invasive. The study wound sites will involve bone and soft tissue.

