The patients will be monitored for 30 days, and will be measured by the amount of post-operative bleeding and overall wound healing for those wounds that can be observed. A base line hemoglobin (HGB) and hematocrit (HCT) blood count, prothrombin time (PT), partial thromboplastin time (PTT), will be drawn and measured 24 hours, and also at 48 hours after surgery. The HGB, HCT, PT and PTT will be drawn 30 days after surgery (Table 1). The patients will be observed and assessed for a minimum of 60 minutes after application of SeraSeal for signs of hypersensitivity to the investigational product, and throughout the 30 days. They will be assessed for, but not limited to, skin rash; wheezing; anaphylaxis; pruritus; prolong coagulation tests; delayed healing or infection through quantitative cultures. In the event there is progression of edema leading to respiratory distress, anaphylaxis, or shock due to blood loss, a crash cart and/or any additional standard and customary treatment(s), will be available. This study will not limit the standard of care performed at both investigational hospitals. The following components of wound care are "standard practice" at each of the hospitals: daily dressing changes; quantitative cultures when infection may be present; routine blood tests. All enrolled study subjects may request to be withdrawn from the study at any time, and will be terminated from the study and provided standard of care. All adverse events will be recorded according to whether the event was unrelated, unlikely, possibly or probably related to the study treatment.

Table 1: Schedule of Assessments

Test	Pre-Op	Surgery	24 Hrs Post Op	48 Hrs Post Op	30 Days
Medical History	X				
Physical Examination	X				
Informed Consent	X				
Designated Delivery System		X			
HGB	X		X*	X+	X
HCT	X		X*	X+	X
PT	X		X*	X+	X
PTT	X		X*	X+	X
ECG	X				
X-Ray Work-UP	X				
Wound care			X	X+	
Microbiological work-up			X*	X+	
Adverse Events			X	X	
Primary Variable		X	X	X	
Secondary Variable		X	X	X	
Safety					
Adverse Events		X	X	X+	X

* measured as often as needed

+ monitored beyond 48 hours as needed

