8.0 Data Analysis:

8.1 Data Collection: There will be one study form for each patient. The surgery form will have all of the outcome data, including blood loss and complications. Once a patient is placed on the surgery schedule, the patient will be asked to participate in the clinical trial by the participating investigator surgeon. The only patients that will require special action are the SeraSeal patients. For those patients the need for SeraSeal will be made known only to the attending surgeon and/or fellows, and made available to the OR room. At the time of the pre-op exam, the inclusion/exclusion of participation in the study will be filled out. The research nurse will collect all data forms and will be responsible for evaluating them for completeness and accuracy, except for time to hemostasis supplied by the surgeon.

8.2 Statistical Analysis: We will compare continuous outcomes such as time to hemostasis (primary outcome), pre and post operative blood loss, surgery duration, (log) bacterial titer, and length of hospital stay in SeraSeal versus conventional treatment, using factorial analysis of variance (ANOVA) methods.

For continuous lab outcomes measured on four occasions (base, 24 hours, 48 hours, 30 days), we will use repeated measure analysis of variance methods to compare mean lab values for conventional versus SeraSeal overall.

For binary outcomes, (including adverse event outcomes) that are not quantified or that may be dichotomized for clinical convenience and interpretability such as fever (yes or no) or pruritus (yes or no) we will use chi-square methods to compare conventional versus SeraSeal treatment proportions overall. Since the total follow up times may differ between groups, we will also compare rates per person-time of binary outcomes under conventional versus SeraSeal treatment overall.

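### The timed hypersensitivity watch starts at SeraSeal application and has no control-arm equivalent, so the comparison of signs such as pruritus and fever is open to a probably modest ascertainment bias against SeraSeal

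*Protocol*

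**What the plan says.** Section 6.6 sets one timed observation for hypersensitivity: "The patients will be observed and assessed for a minimum of 60 minutes after application of SeraSeal for signs of hypersensitivity to the investigational product". The same sentence extends the observation to the 30 days of follow-up. The next step is a list of signs: "They will be assessed for, but not limited to, skin rash; wheezing; anaphylaxis; pruritus", followed by coagulation tests, delayed healing and infection.

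Earlier in the protocol, under the heading on what the study will determine, safety is defined by "recurrence of bleeding, infection, lack of healing, and presence of hypersensitivity reactions, e.g. pruritus, fever, rash, anaphylaxis". Section 7.2 adds that determining the risk of anaphylaxis is one of the study's purposes.

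Section 8.2 then uses signs of this kind as between-arm outcomes: "such as fever (yes or no) or pruritus (yes or no) we will use chi-square methods to compare conventional versus SeraSeal treatment proportions overall". It also plans a comparison of rates per person-time.

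Two statements in section 8.1 bear on who would carry out the watch. One is "The only patients that will require special action are the SeraSeal patients". The other is that "the need for SeraSeal will be made known only to the attending surgeon and/or fellows".

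**The concern.** A between-arm comparison of a yes/no sign is fair only if both arms are looked at in the same way. As written, the hour of observation begins at an event that happens only in the SeraSeal arm. A site that follows the text literally gives that hour to SeraSeal patients and has no instruction to give it to controls. A brief sign in the first hour, such as a transient rash or itching, need not still be visible at the 24-hour assessment. It could be recorded in one arm and missed in the other although the true rates are equal. No later analysis can recover control-arm observations that were not made.

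A second, conditional concern follows from section 8.1. If staff other than the surgeon or fellows carry out the watch, and it is triggered by SeraSeal alone, then being asked to do it reveals the arm to the person scoring the signs. That sits badly with the restriction on who knows the allocation.

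**Working it through.** The protocol gives no figure for the safety comparison, so there is none to reproduce.

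**Step 1: set the passages side by side.**

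| Item | Where | SeraSeal arm | Control arm |
|---|---|---|---|
| Timed watch, at least 60 minutes | 6.6 | From application of SeraSeal | No time zero stated |
| 30-day monitoring | 6.6 | Yes | Yes |
| Adverse events at surgery, 24 h, 48 h, 30 days | Table 1 | Yes | Yes (not split by arm) |
| Time to hemostasis (for contrast) | 6.6 | From first application of product | From first application of control |
| Chi-square on fever, pruritus and the like | 8.2 | Compared | Compared |

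The arms differ in writing only in the first row. The fourth row shows that section 6.6 already uses an arm-neutral starting point for another measurement.

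**Step 2: size of the possible distortion.**

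Inputs from the protocol: 20 per group in each of 5 departments, so 20 × 5 = 100 per arm. The test is the chi-square of section 8.2. The two-sided 0.05 level is carried over from the sample-size paragraph, which concerns the primary outcome.

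Assumptions, none of them in the protocol:
- true incidence *p* = 20% of a minor sign, the same in both arms;
- detection under the watch or equivalent looking, 90%;
- detection *d* of a watch-dependent event without the watch, 50% (70% as an alternative);
- share *s* of events that depend on the first-hour watch, varied.

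Recorded rates:
- SeraSeal: *p* × 0.90 = 0.20 × 0.90 = 18.0%.
- Control: *p* × [(1 − *s*) × 0.90 + *s* × *d*].

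For example, with *s* = 20% and *d* = 50%, the control rate is 0.20 × (0.80 × 0.90 + 0.20 × 0.50) = 0.20 × 0.82 = 16.4%.

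The chance of a falsely significant result against SeraSeal comes from enumerating all pairs of binomial counts (100 per arm). The probabilities are summed where the uncorrected chi-square is significant at 0.05 and SeraSeal has the higher count.

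| Share *s* depending on the watch | Control rate, *d* = 50% | False result against SeraSeal | Control rate, *d* = 70% | False result against SeraSeal |
|---|---|---|---|---|
| 0% (equal looking) | 18.0% | 2.6% | 18.0% | 2.6% |
| 5% | 17.6% | 3.0% | 17.8% | 2.8% |
| 10% | 17.2% | 3.6% | 17.6% | 3.0% |
| 20% | 16.4% | 4.9% | 17.2% | 3.6% |
| 100% | 10.0% | 38% | 14.0% | 12% |

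The nominal figure in this direction is 2.5%. At 10% true incidence, the last row becomes 9% against 5% recorded (19%) and 9% against 7% recorded (8%).

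**Step 3: the effect of equal observation.** With the same detection in both arms, the two-sided false-positive rate stays near 5%: 4.4%, 5.2% and 5.1% at recorded rates of 5%, 10% and 20%.

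**The case against.** The strongest reply is that the protocol already observes both arms. The sentence on the watch reaches over the whole month of follow-up: "observed and assessed for a minimum of 60 minutes after application of SeraSeal for signs of hypersensitivity to the investigational product, and throughout the 30". The paragraph opens with "The patients will be monitored for 30 days", which is not limited to one arm. All adverse events are recorded, and Table 1 schedules them without a split by arm. The hour in question also begins during the operation, when section 7.3 has physicians, nurses and technicians on hand for every procedure. All of this stands. It rules out the reading that hypersensitivity is assessed in SeraSeal patients only; the asymmetry is confined to the timed first hour. It does not supply a control-arm starting point for that hour.

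Three other inferences are tempting and go too far.

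- **That section 8.1 confirms a SeraSeal-only watch.** The sentence on special action is followed at once by text on telling the surgeon and having the product available in the operating room. In context it reads as product supply.
- **That the watch contradicts the single-blind design.** The protocol does not say who is blinded. If it is the patient, staff knowledge contradicts nothing. Nor does it say who performs the watch; the surgeon or fellows, who know the arm, could do so. The tension is with section 8.1, and only if others perform it.
- **That the main safety comparison is affected.** Fever and pruritus are given as examples. Rebleeding, infection and lack of healing are safety outcomes too, and fever is not named among the signs in the section 6.6 list.

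It is also fair to say that a minimum watch after a bovine protein is a product-specific precaution, and that the likely bias would not make SeraSeal look falsely safe. That lowers the stakes, but an estimate tilted against the product still misstates the risk that section 7.2 sets out to determine.

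**Conclusion.** The point holds in a limited form. The timed watch lacks a control-arm time zero while signs it is meant to catch are compared between arms, so the hypersensitivity comparison may be biased by unequal looking. The protocol does not establish that it is biased.

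The likely direction is against SeraSeal and the likely size is modest. Under the stated assumptions, the chance of a false signal rises from about 2.5% to between 3% and 5% when 5% to 20% of events depend on the first hour. A reader might take 38% as the expected error. That figure needs every event over 30 days to depend on a one-hour watch, which the shared follow-up makes implausible. The incidence, the detection fractions and the watch-dependent share are all assumptions.

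The disclosure of the arm is a conditional problem that turns on who carries out the watch. The change is worth making before enrollment because it is cheap and the missing observations could not be collected afterwards.

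**What to change.** - **Section 6.6, time zero.** Count the observation window already stated from first application of SeraSeal or the control method, as the same section does for time to hemostasis. The length of the window is not at issue.
- **Section 6.6, content.** State that the same checklist of signs and the same 30-day assessment apply in both arms. Name fever in the list, since section 8.2 compares it.
- **Scoring.** Say who performs the watch and who is blinded. Where feasible, have existing staff who are not told the arm complete the checklist.
- **Section 8.1.** Make clear that the special action for SeraSeal patients refers to product supply.

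The cost is protocol wording and the same checklist for about 100 control patients during routine recovery, which means a little more nursing record time. No added procedure is needed.

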6.7 Inclusion/Exclusion Criteria

Inclusion criteria:

1. All ages and both genders
2. Wounds of a similar type, size, location and bleeding tendency listed in Table 1.
3. Currently on anticoagulation therapy with no dosage limitations.
4. Diagnosed with a coagulation disorder.
5. Participants must be able to participate for the 30 day duration of the study.

Exclusion criteria:

1. Any clinically infected wound, draining pus, surrounding erythema or edema, or patients with systemic signs of infections.
2. Subjects on antibiotic therapy prior to enrollment.
3. Subjects with known allergy to bovine proteins, atopic reactions, history of anaphylaxis.
4. HIV virus infection
5. Sensitivity to iodine
6. Inability to give informed consent.
7. Inability to return for a 30 day follow-up visit.

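### Prolonged coagulation tests are read as a reaction to SeraSeal, and PT/PTT compared by arm, without tying either to the patient's own baseline or anticoagulant status

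*Protocol*

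**What the plan says.** **The sign.** Section 6.6 has patients observed "for a minimum of 60 minutes after application of SeraSeal for signs of hypersensitivity to the investigational product, and throughout the 30 days". The items to look for follow: "They will be assessed for, but not limited to, skin rash; wheezing; anaphylaxis; pruritus; prolong coagulation tests". No threshold is given, and nothing says whether prolonged means outside a normal range or longer than the patient's own earlier value.

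**The population.** The inclusion list in section 6.7 contains "Currently on anticoagulation therapy with no dosage limitations" and, as a separate item, "Diagnosed with a coagulation disorder". It is not clear whether these two are required of every patient or merely permitted.

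**The measurements.** Section 6.6 and Table 1 schedule PT and PTT before surgery, at 24 and 48 hours, and at 30 days: "prothrombin time (PT), partial thromboplastin time (PTT), will be drawn and measured 24 hours, and also at 48 hours after surgery", with the 30-day draw in the sentence after it.

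**The analysis.** For continuous laboratory outcomes on those four occasions, section 8.2 states "we will use repeated measure analysis of variance methods to compare mean lab values for conventional versus SeraSeal overall". For binary outcomes, adverse events included, it states "we will use chi-square methods to compare conventional versus SeraSeal treatment proportions overall". Neither sentence mentions anticoagulant status or adjustment for the pre-operative value.

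**The concern.** The sign, the population and the comparison do not fit together. In a patient on an anticoagulant or with a coagulation disorder, PT or PTT may be prolonged before SeraSeal is applied, and it may move when therapy changes around surgery. A definition without a baseline cannot separate that from an effect of the product. The error can run either way when an adverse event is graded for relatedness: SeraSeal is blamed for an anticoagulant effect, or a product effect is dismissed as the anticoagulant.

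At group level, the difference between anticoagulated and other patients goes into the error of a raw comparison of means and swamps a modest shift.

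The reading matters here. Section 6.5 gives bovine Factors II, VII, IX and X as the active ingredients, and describes antibody formation after other bovine products. PT and PTT are the only coagulation tests in Table 1, so an effect on clotting factors would have to show there.

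**Working it through.** The protocol states no figure for this point, so there is none to reproduce. The calculation below only shows how large the loss could be.

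**Inputs**
- From the protocol: 200 patients in total, 20 × 2 × 5, hence n = 100 per arm; two-sided α = 0.05 (section 8.2, stated for the primary outcome).
- Assumed, not in the documents: anticoagulated share q = 0.30; PT mean 13 s, SD 1.2 without anticoagulant; mean 26 s, SD 5 with it. SeraSeal shifts PT by 1 s at every post-operative draw. The SDs, and the within-stratum correlation r between draws, are the same throughout. No therapy changes between draws.

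**Step 1: spread of PT in the mixed population**
- Between strata: B = q(1−q)(26−13)² = 0.21 × 169 = 35.49
- Within strata: W = 0.30 × 25 + 0.70 × 1.44 = 8.508
- Total: V = 44.00, SD 6.63 s. The gap between strata makes up 35.49/44.00 = 81% of the variance.

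Power is Φ(δ/SE − 1.96) plus the negligible opposite tail, with SE = √(2 × variance/100).

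**Step 2: single post-operative draw, raw.** SE = √(2 × 44.00/100) = 0.938; 1/0.938 = 1.07; power 19%.

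**Step 3: group effect averaged over all four occasions.** Baseline cannot carry an effect, so the contrast is ¾ × 1 = 0.75 s. The variance is B + W(1+3r)/4. At r = 0.5 it is 40.81, SE 0.903, ratio 0.83, power 13%. At r = 0 and r = 0.7 it is 14% and 13%.

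**Step 4: post-operative draw adjusted for baseline.** Correlation with baseline over all patients is ρ = (B + rW)/V; residual variance is V(1−ρ²).

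| r | ρ | residual variance | SE | power for 1 s |
|---|---|---|---|---|
| 0 | 0.807 | 15.37 | 0.554 | 44% |
| 0.5 | 0.903 | 8.10 | 0.402 | 70% |
| 0.7 | 0.942 | 4.96 | 0.315 | 89% |

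**Step 5: stratified by anticoagulant status, inverse-variance weights.** SEs by stratum are 1.2√(2/70) = 0.203 and 5√(2/30) = 1.291. The combined SE is 1/√(1/0.203² + 1/1.291²) = 0.200; power is over 99%.

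**Step 6: other shares, same formulas**

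| q | four-occasion average | single draw, raw | baseline-adjusted, r = 0 to 0.7 |
|---|---|---|---|
| 10% | 24–26% | 37% | 77% to over 99% |
| 30% | 13–14% | 19% | 44–89% |
| 50% | 11–12% | 16% | 31–72% |

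**Step 7: larger effects.** With q = 0.30 and the raw single-draw SE of 0.938, power is Φ(2/0.938 − 1.96) = 57% for a 2 s shift and Φ(3/0.938 − 1.96) = 89% for 3 s. The raw comparison is insensitive, not blind.

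**The case against.** The strongest case against the point is that the protocol already holds most of what is needed. PT and PTT are drawn before surgery, so existing prolongation is visible. Current medications are recorded at screening. The control arm is randomised and concurrent, so anticoagulant use is expected in both arms. Adverse events are graded for relatedness. A repeated-measures analysis can also be read through its group-by-time term, which uses change from baseline. With variance 2W(1−r), that gives power of 40%, 68% and 88% at r = 0, 0.5 and 0.7, close to Step 4. Thresholds for abnormal laboratory values are commonly left to a statistical analysis plan.

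Much of this stands, and it limits the claim. A reader might infer that SeraSeal's effect on clotting is masked whatever its size; the baseline draws, the randomised control and Step 7 contradict that. A reader might also infer that PT/PTT will be reduced to yes/no and tested by chi-square. Section 8.2 treats laboratory values as continuous and gives fever and pruritus as its binary examples, so a power figure for a yes/no sign would test an analysis that is not stated.

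The objection does not remove the point. The protocol itself names the sign, lists the population and fixes the contrast: "compare mean lab values for conventional versus SeraSeal overall". Nothing directs the reader to change from baseline, and the most direct reading of that wording is the group effect averaged over occasions. Relatedness grading is where an undefined sign does harm, because the grader has no rule for separating the drug or disorder from the product.

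**Conclusion.** The point holds as a loss of sensitivity and a problem of attribution. On the assumed inputs, power for a 1 s PT shift is about 13 to 19% with an overall or single-time raw comparison, against 44 to 89% with baseline adjustment. The direction holds at every share in Step 6, but the size depends on figures that the documents do not give: the anticoagulated share, the PT spread and the correlation between draws. Changes of therapy around surgery would lower the adjusted figures, because the pre-operative value does not capture them.

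Two further inferences are not supported. First, one might let the safety conclusion rest only on patients with neither anticoagulant nor coagulation disorder. Read literally, the inclusion list requires both conditions, and that stratum would be empty; read permissively, the conclusion would leave out patients whom the protocol deliberately admits. Second, one might conclude that every patient has a prolonged baseline test; the documents leave that open. The finding concerns a safety reading and leaves the primary outcome untouched. It merits correction because the remedy uses data already being collected.

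**What to change.** 1. In section 6.6, define the sign as prolongation relative to the patient's own pre-operative PT or PTT, with the amount of change fixed in advance, and apply it identically in both arms.
2. In section 8.2, replace the overall comparison of mean PT/PTT with a between-arm comparison of post-operative values. Adjust it for the pre-operative value and stratify by pre-operative anticoagulant or coagulation-disorder status. Keep all patients in the safety analysis and also show results by stratum.
3. State that the pre-operative value does not remove changes in anticoagulant therapy around surgery, and note anticoagulant use at each draw from the patient's record.
4. Clarify whether the two coagulation items in section 6.7 are required or permitted, since the strata depend on it.

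The cost is wording, slightly more analysis work and an entry from the record at each draw. No new blood test or visit is needed. The strata will each be smaller than 100 per arm, so results by stratum will be less precise than the combined adjusted estimate.
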